1.2.2 Phase 3 Pivotal Studies ARC003, ARC010, and ARC007

ARC003 was an international, randomized, double-blind, placebo-controlled phase 3 study of the efficacy and safety of AR101 in peanut-allergic children and adults aged 4 to 55 years ([PALISADE group of clinical investigators, 2018](#)). The study consisted of a screening phase (including a DBPCFC), a double-blind OIT treatment phase (including initial dose escalation [2 days], up-dosing [20-40 weeks], and maintenance [approximately 6 months]), and an exit DBPCFC. Of 555 subjects enrolled, 499 subjects were aged 4 to 17 years. The ITT population for the primary analysis included 496 subjects aged 4 to 17 years (372 in the AR101 group and 124 in the placebo group); 67.2% of AR101-treated subjects tolerated a single dose of at least 600 mg peanut protein (1043 mg cumulative) with no more than mild symptoms in the exit DBPCFC compared with 4.0% of placebo-treated subjects, resulting in a treatment difference of 63.2% (95% CI: 53.0, 73.3; $p < 0.0001$). In addition, 50.3% of AR101-treated subjects tolerated a single dose of 1000 mg peanut protein (2043 mg cumulative), compared with 2.4% of placebo-treated subjects (95% CI: 38.0, 57.7; $p < 0.0001$). Of subjects aged 4 to 17 years, 296 AR101-treated subjects and 116 placebo-treated subjects had an evaluable exit DBPCFC (ie, completed at least the peanut food challenge day; completer population). A single dose of peanut protein was tolerated with no more than mild symptoms in the exit DBPCFC by 96.3% of AR101-treated completers versus 8.6% of placebo completers for at least 300 mg (443 mg cumulative), 84.5% versus 4.3% for at least 600 mg (1043 mg cumulative), and 63.2% versus 2.6% for 1000 mg (2043 mg cumulative).

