Adverse event or intercurrent illness	
Any intolerable adverse event that cannot be ameliorated using adequate medical intervention or that in the opinion of the investigator or sponsor may lead to undue risk if study treatment were continued, such as the following:
 
• Life-threatening symptoms (CoFAR grade 4), including anaphylaxis resulting in hypotension, neurologic compromise, or mechanical ventilation secondary to study treatment or food challenge.• Severe dose-related allergic hypersensitivity symptoms (CoFAR grade 3) that require intensive therapy (per investigator assessment, but may include interventions such as IV epinephrine, intubation, or admission to an intensive care unit) or are recurrent.• Poor control or persistent activation of secondary atopic disease (eg, atopic dermatitis, asthma).• Development of biopsy-documented eosinophilic esophagitis. 
Any adverse event that meets the early discontinuation criteria for study product tolerability or delays as follows:
 
• Tolerability of study product:
– Dose-limiting, moderate, or severe symptoms at any dose on initial dose-escalation day 1 or 2– Dose withheld for > 4 weeks for chronic or recurrent gastrointestinal adverse events at ≤ 20 mg/day– Unable to tolerate the 300 mg/day dose for 2 weeks within 40 weeks of up-dosing• Use of rescue medications:
– Treatment with epinephrine, beta-agonist, oxygen, IV fluids, > 2 doses of antihistamines, and/or glucocorticosteroids at any study product dose on initial dose-escalation day 1 or 2

Category Reason	Comment on Criteria

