10.2 Analysis Populations

The ITT population (ie, full analysis set) will be defined as all subjects who receive any part of 1 dose of study product. The ITT population will be used for all efficacy analyses unless otherwise specified, and analyzed according to randomized treatment. If no subjects receive the incorrect treatment, the ITT population will be the same as the safety population.

The completer population will be defined as all subjects in the ITT population who complete study treatment and have an evaluable exit DBPCFC (completion of at least the peanut food challenge day).

The per protocol population may be defined if it is sufficiently different from the completer population. The per protocol population will include all subjects in the completer population who have no major protocol deviations that may influence the desensitization response.

The safety population will be defined as all subjects who receive any randomized study treatment (ie, who receive any part of 1 dose of study product and complete 1 study visit). The safety population will be used for all safety analyses and analyzed according to treatment received.

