10.5 Analysis of Efficacy

10.5.1 Primary Efficacy Analyses

The primary objective assesses the efficacy of AR101 treatment in peanut-allergic subjects aged 1 to < 4 years.

The primary efficacy endpoints are defined by major health authority region.

- **North America:** The primary efficacy endpoint is the proportion of subjects treated with AR101 compared with placebo who tolerate an at least 600 mg single dose of peanut protein with no more than mild allergy symptoms during the exit DBPCFC.
- **Europe:** The primary efficacy endpoint is the proportion of subjects treated with AR101 compared with placebo who tolerate an at least 1000 mg single dose of peanut protein with no more than mild allergy symptoms during the exit DBPCFC.

The ITT population and Farrington-Manning test will be used for these analyses. Subjects tolerating a single dose of at least 600 mg peanut protein for North America and at least 1000 mg peanut protein for Europe will be considered responders; subjects who do not tolerate a single dose of at least 600 mg peanut protein for North America and at least 1000 mg peanut protein for Europe will be considered nonresponders. Nonresponders will also include subjects who withdraw consent or discontinue early anytime before the exit DBPCFC.

Desensitization response rates and associated 95% CIs will be presented for each treatment group using exact Clopper-Pearson CIs. The 95% CI for the treatment difference (desensitization rate for AR101 treatment minus desensitization rate for placebo) will be based on the Farrington-Manning method. The primary efficacy endpoint for North America will be considered met if the lower bound of the 95% CI is greater than the prespecified margin of 0.15. The primary efficacy endpoint for Europe will be considered met if the lower bound of the 95% CI is greater than 0.

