5 STATISTICAL METHODS

Changes to the statistical methods and data presentations for reporting the study due to any restrictions will be detailed in the statistical analysis plan.

Limits to the prespecified maximum duration of up-dosing and maintenance periods for subjects to meet the criteria of responders at the exit food challenge will continue to apply, with the exception of any duration of time affected by the restrictions as defined by the first and last consecutively affected study visits. For instances of multiple distinct durations of

restriction, the maximum duration of the up-dosing and maintenance periods will be extended by the cumulative sum of these distinct durations of affected study visits.

Subjects who discontinue early from the study for any reason before completing their scheduled exit food challenge, including due to the restrictions, will be counted as nonresponders in an intent-to-treat analysis, and may also be excluded from an alternative sensitivity analysis of the primary and prespecified secondary endpoints as appropriate.

Additional subjects may need to be enrolled to accommodate a potential increase in dropouts, a substantial extension of the up-dosing period, or a substantial delay in completion of exit food challenges. In the event a greater than anticipated number of subjects discontinue early from the study due to the restrictions, the study sample size may be increased by up to 20% without protocol amendment. The sponsor may perform one or more blinded sample size reassessments, potentially in consultation with an external unblinded data and safety monitoring committee, to address any safety concerns associated with an increase in the study sample size.

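### Appendix 3 permits a sensitivity analysis that drops early discontinuers whatever their reason, which nearly repeats the completer analysis and cannot separate restriction-related dropout from treatment failure

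*Combined protocol and SAP*

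**What the plan says.** Appendix 3, Section 5 (Statistical Methods) defines the group as "Subjects who discontinue early from the study for any reason before completing their scheduled exit food challenge, including due to the restrictions". These children "will be counted as nonresponders in an intent-to-treat analysis", and they "may also be excluded from an alternative sensitivity analysis of the primary and prespecified secondary endpoints as appropriate". The same section leaves changes of method caused by restrictions to the statistical analysis plan.

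The main text takes the same line on the primary analysis. Section 10.5.1 states: "Nonresponders will also include subjects who withdraw consent or discontinue early anytime before the exit DBPCFC".

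Section 5.3, Table 4 lists the primary reasons for early discontinuation. They include adverse events and failure to tolerate study product, for example "Unable to tolerate the 300 mg/day dose for 2 weeks within 40 weeks of up-dosing". No category refers to pandemic or emergency restrictions.

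Section 10.2 already has a set that leaves out early stoppers: "The completer population will be defined as all subjects in the ITT population who complete study treatment and have an evaluable exit DBPCFC".

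**The concern.** A sensitivity analysis for disruption should ask one question: how far does the primary result depend on counting as failures those children who stopped only because of the restrictions? Answering it means treating those children differently and everyone else the same.

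The Appendix 3 sentence attaches the optional exclusion to all early discontinuers. A child who stops because of reactions to AR101 is a treatment failure, and the primary analysis counts that child as one. Removing such children conditions on something that happens after randomisation and is likely to differ between arms. Section 1.2.2 reports that about 10% of ARC003 subjects aged 4 to 17 stopped for adverse events, mostly gastrointestinal events during up-dosing (not split by arm).

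A larger difference from this analysis could then be presented as evidence that disruption had diluted the effect, when much of the increase comes from removing treatment failures.

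**Working it through.** **1. The plan's own figure.** Inputs from Section 10.3 and Section 10.5.1: 88 AR101 and 44 placebo, 55% against 15%, margin 0.15, two-sided 0.05. Under the Farrington-Manning null the restricted rates are 0.458 and 0.308.
- Null SE = √(0.458×0.542/88 + 0.308×0.692/44) = 0.0875
- Alternative SE = √(0.55×0.45/88 + 0.15×0.85/44) = 0.0756
- Power = Φ[(0.40 − 0.15 − 1.96×0.0875)/0.0756] = 85.0% (85.4% by exact enumeration), against 85% stated

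For Europe (50% against 10%, null 0) the result is 99.9%, against more than 95% stated. The planning rates are therefore read correctly. Section 10.3 says they already count dropouts, estimated at 25% overall, as nonresponders.

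**2. Effect of excluding every discontinuer.** Discontinuers contribute no responders, so an ITT rate p with dropout d becomes p/(1 − d).

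| Dropout, AR101 / placebo | North America | Europe |
|---|---|---|
| ITT, none excluded | 55.0 − 15.0 = 40.0 | 50.0 − 10.0 = 40.0 |
| 25% / 25% | 73.3 − 20.0 = 53.3 | 66.7 − 13.3 = 53.3 |
| 32.4% / 10.2% | 81.3 − 16.7 = 64.6 | 73.9 − 11.1 = 62.8 |

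The last row is an assumption. It keeps 25% overall (33 of 132) and splits it in the ARC003 ratio from step 4, 20.4/6.5 ≈ 3.17.

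**3. Effect of excluding restriction-related stops only.** Let r be the share of each arm that stops because of the restrictions, within the 25%. The plan gives no r, so 5% to 15%, equal in both arms, is assumed. The North America difference becomes 40.0/(1 − r).
- r = 5%: 42.1 points, so the wider exclusion adds 11.2
- r = 10%: 44.4 points, so it adds 8.9
- r = 15%: 47.1 points, so it adds 6.3

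Those added points have nothing to do with the restrictions.

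**4. ARC003 (Section 1.2.2).** The ITT sizes are 372 and 124, and "296 AR101-treated subjects and 116 placebo-treated subjects had an evaluable exit DBPCFC". The shares without one are 76/372 = 20.4% and 8/124 = 6.5%. Responder counts are back-calculated from the reported percentages.
- 600 mg: 250/372 − 5/124 = 63.2 points, as reported. Among evaluable subjects, 250/296 − 5/116 = 80.1 points.
- 1000 mg: 187/372 − 3/124 = 47.8 points. Among evaluable subjects, 187/296 − 3/116 = 60.6 points.

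**5. Direction.** Dropout of 15% on AR101 and 45% on placebo (assumed; also 25% overall) gives 55/0.85 − 15/0.55 = 64.7 − 27.3 = 37.4 points, below 40.0. At 20% and 35% the result is 45.7, still above. Reversal needs much heavier placebo dropout.

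**6. Behaviour at the margin.** Suppose the true ITT rates are 30% and 15%, exactly at the 0.15 margin. By exact enumeration of the Farrington-Manning test, the chance that the lower bound exceeds 0.15 is:
- ITT, 88 and 44: 2.3%
- All discontinuers excluded, 25% in each arm (66 and 33): 7.0%
- ARC003 dropout of 20.4% and 6.5% (70 and 41; rates 37.7% and 16.0%): 12.2%
- 25% overall, split as in ARC003 (60 and 40): 27.5%

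**The case against.** The strongest reply is that the sentence only permits the exclusion, and only where appropriate. That leaves room to remove restriction-related stops alone, with the detail left to the SAP. This stands as far as it goes. A reader might infer that the plan requires every discontinuer to be dropped, or that no other disruption analysis exists; the available text supports neither. The permission still covers everyone who stops early, and nothing in the text narrows it. Under Section 3.3 treatment is unblinded subject by subject, so an open choice of set is poorly protected.

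Other stronger readings also go too far:
- **That the exclusion always favours AR101.** Step 5 shows a reversal.
- **That the analysis is uninformative about restriction-related dropout.** Those children are among the ones removed. Their effect is mixed with that of the others, not absent.
- **That the right analysis could not be run.** Table 4 lacks a category, but the case report form was not available. Appendix 3 already separates pandemic-related reasons from noncompliance for missed doses. It also allows up to 20% more subjects if restriction-related discontinuations exceed expectation, which implies that they are counted.
- **That step 6 shows type I error inflation.** Primary success and the secondary hierarchy rest on the ITT analysis, and no claim is attached to this one.

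ARC003 also has limits as a guide. It enrolled older children, and lacking an evaluable exit challenge is not quite the same as discontinuing. Completer results are openly planned and legitimate when labelled as such.

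**Conclusion.** The point holds as a defect in a supportive analysis. As worded, Appendix 3 permits an analysis close to the completer analysis. It is not quite identical, because Section 10.2 needs only the peanut challenge day whereas Section 5.3 counts stopping at any time before the exit challenge is complete. Used that way, it cannot distinguish disruption from intolerance.

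On the planning rates with equal 25% dropout, it adds 13.3 points to the North America difference. Restriction-only exclusion adds 2.1 to 7.1 points, assuming 5% to 15% of each arm stop for that reason. If dropout splits between arms as in ARC003, the full exclusion adds 24.6 points. Upward movement is likely, given the ARC003 pattern, but not guaranteed. The arm-specific dropout and the restriction-related share are assumptions. The primary ITT result is untouched, and the SAP may already define a narrower set.

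**What to change.** In Appendix 3 Section 5:
- Limit the exclusion to children whose primary reason for stopping is documented as the restrictions before that child's treatment is unblinded.
- Keep every other early discontinuer (adverse event, intolerance, noncompliance, family decision, loss to follow-up) as a nonresponder.
- If an analysis excluding all discontinuers is also wanted, label it as the completer analysis.

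Add a restriction-related reason to Table 4 and to the disposition form, and carry the same rule into the SAP. Multiple imputation for the restriction-related group is an option, not a necessity.

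The cost is a short change of wording and one reason code. The sensitivity estimate will usually be less favourable to AR101 than the completer figure.

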6 STUDY MONITORING

Study monitoring will be conducted remotely until onsite study monitoring visits can resume.

Appendix 4: Study Schedule of Activities: Screening (Days -42 to -1)

Activity	Comments
General	Complete screening procedures within 42 days after obtaining signed consent (and assent where required).
Informed consent, subject ID number	Obtain consent (and assent where required) before performing any study-specific procedures. Ensure consent is on current version of form reviewed by the ethics committee.
Questionnaire	Instruct parent/caregiver to complete TRACK (for subject with asthma) before the DBPCFC on both days of the screening DBPCFC.
Demographics, medical history	Includes allergy history (including anaphylactic reactions) and symptoms, and diet/food allergen history.
Weight, height	
Vital signs	Measure blood pressure, heart rate, temperature, respiratory rate, and oxygen saturation level.
Asthma evaluation	For subject with asthma. Evaluate asthma severity per NHLBI 2007 criteria (Table 16) before the DBPCFC on both days of the screening DBPCFC.
EASI score	For subject with eczema or atopic dermatitis. Assess eczema or atopic dermatitis.
Food allergy instruction	Provide food/peanut allergy education (including recognition of an allergic reaction, symptoms of anaphylaxis, administration of epinephrine auto-injector, anaphylaxis action plan, ways to minimize accidental exposure to peanut) per standard of care at the study site. Verify that parent/caregiver has an epinephrine auto-injector, including appropriate dose and expiry. Instruct that subject is to avoid peanut during the study. Document the discussion in the subject's source records.
Complete physical examination	Assess systems (eg, general appearance, head, eyes, ears, nose, mouth, skin, heart, lungs, lymph nodes, gastrointestinal, genitourinary, neurologic, and skeletal).
Pretreatment adverse event review	Record adverse event information (including allergy symptoms) from the time of signed informed consent/assent.
Concomitant medications review & instruction	Record all medications taken within 90 days before screening. Instruct that subject is to discontinue antihistamines and other medications that could interfere with the assessment of an allergic reaction 5 half-lives of the medication before the screening skin prick test and DBPCFC, and first dose of dose escalation. Review the prescribing information to determine the half-life of each medication for the subject's relevant age group.
Skin prick test	Perform before the DBPCFC begins (same day or any previous day are acceptable). Measure mean wheal diameter and mean erythema diameter for peanut extract.

Activity	Comments
Laboratory Evaluations	Refer to the laboratory manual for sample collection and processing.
Hematology, immunology	Collect blood sample before the DBPCFC begins (same day or any previous day are acceptable). The total volume of blood collected is not to exceed 2 mL/kg per day (maximum 4 mL/kg in a 30-day period) or per local requirements. Complete blood count with differential. Total, peanut-specific, and peanut component-specific IgE. Peanut-specific and peanut component-specific IgG4.
Optional blood sample for evaluation of cellular responses to peanut antigen	At certain study sites only. Collect before the DBPCFC begins (same day or any previous day are acceptable).
DBPCFC and Eligibility Confirmation	
DBPCFC	Conduct on 2 separate days within 7 days. Measure vital signs and assess signs/symptoms of allergic reaction just before each challenge dose, and at least every 15-20 minutes postdose if the dosing interval between challenge dosing is prolonged. Refer to Appendix 1 for details.
Eligibility Confirmation	Confirm eligibility after completion of all screening activities.

DBPCFC, double-blind, placebo-controlled food challenge; EASI, Eczema Area and Severity Index; ID, identification; Ig, immunoglobulin; NHLBI, National Heart, Lung, and Blood Institute; TRACK, Test for Respiratory and Asthma Control in Kids.

Appendix 5: Study Schedule of Activities: Treatment (Initial Dose Escalation, Up-Dosing, and Maintenance)

- [1] Day 1 activities must begin within 42 days after obtaining signed consent and assent (where required) and within 10 days after the second day of the screening DBPCFC. The timing of day 1 study product administration, vital signs, and assessment of allergic reactions for initial dose escalation is presented in [Table 2](#).
- [2] Day 2 should be the next consecutive day after day 1. Day 2 may be delayed up to 7 days after day 1 if unexpected circumstances (eg, an intercurrent illness) create a safety risk.
- [3] Anytime necessary to assess or follow up adverse events, at the request of the parent/caregiver, or per investigator decision. Perform procedures as appropriate.
- [4] Early discontinuation: For subject who discontinues treatment early; approximately 14 days after the last dose.
Exit: For subject who completes initial dose escalation, up-dosing, and maintenance for an overall total of approximately 12 months of treatment, and both days of the exit DBPCFC. If the follow-on study is not yet available at the study site, blinded study treatment may continue and the visit schedule will be every 4 weeks until the follow-on study is available.
For subject not enrolling in the follow-on study, the exit visit is approximately 14 days after the last dose.
- [5] The first maintenance visit will occur after 300 mg/day is tolerated for 2 weeks during up-dosing. Maintenance treatment will continue daily for an overall total of approximately 12 months of treatment. The duration of maintenance treatment may vary from a minimum of 12 weeks to a maximum of 24 weeks depending on the up-dosing interval (24-40 weeks).
- [6] For subject with asthma. Instruct parent/caregiver to complete TRACK at the start of the visit before other procedures and before the DBPCFC on both days of the DBPCFC.
- [7] Vital signs include blood pressure, heart rate, temperature, respiratory rate, and oxygen saturation level. Measure predose, at 15-30 minutes postdose, and every approximately 30 minutes thereafter (until at least 90 minutes postdose or end of observations for allergy symptoms, whichever is last). During maintenance treatment, the postdose observation period may be shortened to approximately 30 minutes if no allergy symptoms occurred during the previous 3 maintenance visits.
- [8] For subject with asthma. Evaluate asthma severity per 2007 NHLBI criteria ([Table 16](#)). Evaluate asthma before the DBPCFC on both days of the DBPCFC.
- [9] For subject with eczema or atopic dermatitis. Assess eczema or atopic dermatitis.
- [10] Perform/collect at early discontinuation visit or before the exit DBPCFC begins (same day or any previous day within the exit visit window are acceptable).
- [11] Symptom-directed: Assess systems per standard of care at the study site or as clinically indicated by symptoms.
Complete: Assess systems (eg, general appearance, head, eyes, ears, nose, mouth, skin, heart, lungs, lymph nodes, gastrointestinal, genitourinary, neurologic, and skeletal).
- [12] Instruct that subject is to avoid peanut during the study. Provide food/peanut allergy education (including recognition of an allergic reaction, symptoms of anaphylaxis, administration of epinephrine auto-injector, anaphylaxis action plan, ways to minimize accidental exposure to peanut) per standard of care at the study site.
- [13] Include review of symptoms recorded in subject diary. For subject with GI adverse events of interest, instruct parent/caregiver to complete the PEESS v2.0 questionnaire while subject is symptomatic, at early discontinuation or study exit, and during safety follow-up. Subject with unresolved adverse events at early discontinuation or exit and subject with GI adverse events of interest will have safety follow-up per [Appendix 6](#).

- [14] Review medications since previous visit. Instruct that subject is to discontinue antihistamines and other medications that could interfere with the assessment of an allergic reaction 5 half-lives of the medication before initial dose-escalation day 1, skin prick tests, and the exit DBPCFC. Review the prescribing information to determine the half-life of each medication for the subject's relevant age group.
- [15] Administer study product at the study site per the dose-escalation schedules and dose modification guidelines. Measure vital signs and assess signs/symptoms of allergic reaction at 15-30 minutes postdose and every approximately 30 minutes thereafter (until at least 90 minutes postdose or end of observations for allergy symptoms, whichever is last). During maintenance treatment, the postdose observation period may be shortened to approximately 30 minutes if no allergy symptoms occurred during the previous 3 maintenance visits.
- [16] Review instructions for administration of study product at home. Instruct that subject withhold study product when it will be administered at the study site and on the days of the exit DBPCFC.
- [17] Contact parent/caregiver by telephone for adverse events review and to inquire about compliance with study product dosing on the day after initial dose-escalation day 2, up-dosing visits, maintenance visits, and the exit DBPCFC. Remind parent/caregiver to record symptoms in the diary (except after completion of the exit DBPCFC).
- [18] For subject who completes an overall total of approximately 12 months of treatment and tolerates the 300 mg daily dose of study product for at least 2 consecutive weeks before having the exit DBPCFC. Conduct on 2 separate days within 7 days.
- [19] Refer to the laboratory manual for sample collection and processing.
- [20] Complete blood count with differential. Total, peanut-specific, and peanut component-specific IgE. Peanut-specific and peanut component-specific IgG4.

DBPCFC, double-blind, placebo-controlled food challenge; EASI, Eczema Area and Severity Index; ED, early discontinuation; GI, gastrointestinal; Ig, immunoglobulin; na, not applicable; NHLBI, National Heart, Lung, and Blood Institute; opt, optional; PEESS v2.0, Pediatric Eosinophilic Esophagitis Symptom Scores version 2.0; q, every; TRACK, Test for Respiratory and Asthma Control in Kids; unsch, unscheduled; w, weeks.

